Neuromuscular toxicity	Peripheral sensory neuropathy, muscle weakness, Guilliain- Barre syndrome, transverse myelitis, myasthenia gravis	 Physical exam of sensory change, loss of deep- tendon reflexes Neuroimaging, nerve conduction exam 	≤ Moderate (Grade 2): administration of corticosteroids at a dose of 1-2 mg/kg/day prednisone equivalents	Withhold CS1001 until resolved to ≤ Grade 1
	 conduction exam Nerve/muscle biopsy 		≥ Severe (Grade 3): high dose corticosteroids (2-4 mg/kg/day IV methylprednisolone)	Permanent discontinuation from the study treatment

Potential irAE	Potential signs and symptoms	Diagnosis and differential diagnosis	Recommended management	Dose modification
Ocular toxicity	Photosensitivity, pain or dryness of the eyes, blurred vision, uveitis, iritis, episcleritis	• Ophthalmic exam	≤ Moderate (Grade 2): topical steroids (1% prednisolone)	Withhold CS1001 until resolved to \leq Grade 1; if not resolved \leq Grade 1 within 14 days with topical steroids or initiation of systemic treatment, permanent discontinuation from the study treatment
			≥ Severe (Grade 3): high dose corticosteroids (2-4 mg/kg/day IV methylprednisolone)	Permanent discontinuation from the study treatment
Other irAEs, such as arthritis, pancreatitis, hemolytic anemia,			Moderate (Grade 2)	Withhold CS1001 until resolved to \leq Grade 1
adrenal insufficiency, myasthenic syndrome, and rhabdomyolysis			≥ Severe (Grade 3)	Permanent discontinuation from the study treatment

13.5PROTOCOL AMENDMENT

Major amendments in protocol Version 3.0

Section(s)	Title of section(s)	Amendment details	Amendment rationale
SYNOPSIS	Secondary endpoints	Move 6 month PFS and 6 month OS rate from secondary endpoints to exploratory endpoints,	In single-arm trials, time-to-event efficacy endpoints such as PFS and OS
	Secondary efficacy analyses	details refer to Protocol Amendment 3.0	should be exploratory rather than secondary endpoints
	Exploratory endpoints		secondary enapoints
	Exploratory efficacy analyses		

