4.3 Discontinuation and Withdrawal

4.3.1 Discontinuation of Study Treatment

Subjects must discontinue study treatment if any of the following criteria are met:

- 1. Any AE that meets the treatment discontinuation criteria specified in the protocol (refer to Section 5.3).
- 2. Disease progression. (Subject who meets the criteria for treatment beyond progression may continue treatment until confirmation of progressive disease by tumor assessment. Refer to Section 3.1.2.1.)
- 3. Subjects who receive any prohibited treatment during the trial that compromises the assessment of safety and efficacy may be determined to discontinue study treatment by the investigator in consultation with the sponsor medical monitor.
- 4. Any intercurrent condition that compromises the subject's ability to continue study treatment.
- 5. Pregnancy of female subjects.
- 6. Subjects and/or their legal guardian who decide to discontinue the study treatment may inform the subject's doctor at any time and then discontinue study treatment. According to the Deceleration of Helsinki and other applicable regulatory requirements, all subjects have the right to withdraw from the study at any time and for any reason. The doctor and the study site must not hold bias in their future treatment.
- 7. Subject with poor compliance who doesn't receive treatment at the right dose and the right time despite the investigator's effort in communication and coordination, which may lead to significant uncorrectable bias in the study results may be determined to discontinue study treatment by the investigator in consultation with the sponsor medical monitor.
- 8. Other conditions that make study treatment continuation inappropriate judged by the investigator.

In any case, the primary reason for study treatment discontinuation will be recorded in the original medical record. For subjects who discontinue study treatment for any reason, the investigator should try every effort to have the subject complete end of study visit if the subject has received at least one dose of the investigational product, and continue to follow up subjects with unresolved AE.

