5.3 INVESTIGATIONAL PRODUCT DOSING MODIFICATION

5.3.1 Overall Principle for Investigational Product Dosing Modification

The mechanism of CS1001 is to promote T-cell activation and proliferation. As a result, CS1001 may induce autoimmune hyperactivity which will further cause autoimmune diseases involving multiple organ systems. Immune-related AEs (irAEs), for example, pneumonitis, diarrhea/enterocolitis, renal impairment, rash, hepatitis, endocrine disorders, and peripheral or central neuropathy have occurred in the clinical use of other immune checkpoint inhibitors including ipilimumab, nivolumab, pembrolizumab, and atezolizumab. Once a subject develops any of the above AEs in this trial, the subject should be monitored for symptoms and signs. Appropriate tests and examinations may be conducted for differentiating etiology. If no other cause (for example disease progression, concomitant medication, or infection) is found while the subject requires corticosteroid and/or other immunosuppressive treatment, the AE is considered as related to the immune system hyperactivity caused by CS1001, and thus is an irAE. (This rule doesn't apply to endocrinology events, for example, hyperthyroidism/hypothyroidism, hypophysitis, type I diabetes mellitus, and adrenal insufficiency, which will still be considered as related to autoimmune hyperactivity caused by CS1001 treatment although they may not require immunosuppressive treatment). Identification, diagnosis, management, and dose modification for irAEs are detailed in Appendix 13.4.

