5.3.2 Criteria for Dose Modification of Investigational Product

Dose increase or reduction of CS1001 is not permitted in this trial. The investigational product will be **withheld** for any of the following investigational drug-related adverse reactions:

- 1. Grade 2 pneumonitis
- 2. Grade 2 or 3 colitis; Grade 3 diarrhea or persistent Grade 2 diarrhea
- 3. Grade 2 hepatitis (elevation of ALT, AST, or total bilirubin levels)
- 4. Grade 2 hypophysitis without adrenal crisis
- 5. Grade 2 nephritis
- 6. Grade 3-4 hypothyroidism
- 7. Grade 3 hyperthyroidism lasting for 6 weeks or more despite proper management
- 8. Grade 3 dermatitis
- 9. Grade 2 neuromuscular toxicity
- 10. Grade 2 ocular toxicity
- 11. Other Grade 2 AEs (for example arthritis, pancreatitis, hemolytic anemia, adrenal insufficiency, myasthenic syndrome, and rhabdomyolysis)
- 12. Grade 4 hematologic toxicity
- 13. Any Grade 3 abnormal laboratory test results except for the following situations:
 - Grade 3 hematologic toxicity.

- Study treatment will be delayed when Grade 2 hepatitis occurs.
- 14. Any AE, abnormal laboratory test result, or intercurrent condition that in the investigator's opinion requires postponing study treatment.

Subjects may resume investigational treatment when the above AE(s) resolve(s) to Grade 0/1 or baseline and the dose of systemic corticosteroid for treating the AE(s) have been tapered to 10 mg daily prednisone equivalents or less.

The investigational treatment will not be resumed for dosing delay due to any cause for more than **9 weeks** (12 weeks after the last dose). (Subject may continue treatment if he/she still benefits clinically at the discretion of investigator in consultation with the sponsor's medical monitor.)

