Potential irAE	Potential signs and symptoms	Diagnosis and differential diagnosis	Recommended management	Dose modification
			≥ Severe (Grade 3): administration of corticosteroids at a dose of 1-2 mg/kg/day prednisone equivalents	Permanent discontinuation from the study treatment
Hypothyroidism /hyperthyroidism	Typically asymptomatic and is identified by lab tests	Triiodothyronine (T3), thyroxine (T4) and thyroid stimulating hormone (TSH) test results	Asymptomatic ≤ moderate (Grade 2) hypothyroidism: thyroxine replacement therapy	Continue dosing
			Asymptomatic ≤ moderate (Grade 2) hyperthyroidism: consider beta blockade	Continue dosing
			≥ Severe (Grade 3) hypothyroidism: replacement therapy	Withhold CS1001 until resolved to \leq Grade 1 or baseline
			Severe (Grade 3) hyperthyroidism lasting ≥ 6 weeks despite active management: administration of corticosteroids at a dose of 1-2 mg/kg/day prednisone equivalents	Withhold CS1001 until resolved to ≤ Grade 1
			Life-threatening (Grade 4) hyperthyroidism	Permanent discontinuation from the study treatment
Dermatitis	Maculopapular rash or erythroderma, pruritus, skin ulceration, bullous dermatitis, Stevens-Johnson syndrome	 Unless an alternative etiology is identified, it should be considered immune-related Pathologic evaluation of skin biopsy can be 	≤ Moderate (Grade 2) (up to 30% of body surface area): topical corticosteroids and oral over-the-counter antihistamines and systemic corticosteroids if no improvement within 7 days	Continue dosing

Confidential

Potential irAE	Potential signs and symptoms	Diagnosis and differential diagnosis	Recommended management	Dose modification
		performed to rule out alternative etiology	Severe (Grade 3, > 30% of body surface area): administration of corticosteroids at a dose of 1-2 mg/kg/day prednisone equivalents	Withhold CS1001 until resolved to ≤ Grade 2
			Life-threatening (Grade 4, for example Stevens-Johnson syndrome, toxic epidermal necrosis, full-thickness dermal ulceration, necrosis or hemorrhage): high dose corticosteroids (2-4 mg/kg/day IV methylprednisolone); in-subject hospitalization; consultation with a dermatologist	Permanent discontinuation from the study treatment

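### Grade 3 dermatitis has two incompatible restart rules, in Protocol 5.3.2 and Appendix 13.4, and nothing says which governs

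*Protocol*

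**What the plan says.** **Dermatitis.** Protocol 5.3.2, item 8, puts "Grade 3 dermatitis" on the list of events for which CS1001 is withheld. One restart paragraph then covers the whole list: "Subjects may resume investigational treatment when the above AE(s) resolve(s) to Grade 0/1 or baseline", with the added condition that "the dose of systemic corticosteroid for treating the AE(s) have been tapered to 10 mg daily prednisone equivalents or less". In Appendix 13.4 the Grade 3 dermatitis cell reads "Withhold CS1001 until resolved to ≤ Grade 2" and does not mention the taper.

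**The link between the two texts.** Section 5.3.1 says: "Identification, diagnosis, management, and dose modification for irAEs are detailed in Appendix 13.4". Section 4.3.1, item 1, sends sites to Section 5.3 for the discontinuation criteria. Neither says what to do where Section 5.3 and the Appendix differ.

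**Ocular toxicity.** Section 5.3.2, item 10, withholds for "Grade 2 ocular toxicity" under the same general restart paragraph. Section 5.3.3 makes only Grade 3-4 ocular toxicity a permanent stop by grade, and asks that a stop be considered when Grade 2 or higher recurs. The Appendix row for Grade 2 or less adds a permanent stop if the event has not reached Grade 1 or less in 14 days. That condition also refers to the start of systemic treatment.

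**The concern.** These rules decide whether a patient gets another dose of a checkpoint inhibitor after a severe skin event. A site that works from 5.3.2 and a site that works from the Appendix table can each follow the protocol as written and act in opposite ways on the same rash. Conduct then varies by site on a safety rule, and monitoring has no clear standard for calling a deviation. The SAP (Safety Analyses, Adverse Events) summarizes TEAEs leading to interruption or discontinuation, so the difference can also reach a descriptive table. The primary ORR analysis is not at issue.

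**Working it through.** There is no planned figure to reproduce; the check is a comparison of texts and a count.

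**Step 1. Apply both rules to a Grade 3 rash that is improving.**

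| Rash now | Baseline | Steroid (prednisone equivalent) | 5.3.2 | Appendix 13.4 cell |
|---|---|---|---|---|
| Grade 3 | any below 3 | any | hold | hold |
| Grade 2 | 0/1 | 10 mg/day or less | **hold** | **may dose** |
| Grade 2 | 2 | 10 mg/day or less | may dose | may dose |
| Grade 0/1 | 0/1 | 10 mg/day or less | may dose | may dose |

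The rules conflict in the second line. They agree at residual Grade 2 only if baseline was itself Grade 2, because 5.3.2 accepts a return to baseline.

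**Step 2. Ask whether the specific text can be taken to override the general one.** It cannot settle the matter here. Section 5.3.2 lists Grade 3 dermatitis by name, so both texts are specific to the event. The pointer in 5.3.1 makes the Appendix reachable but sets no order of precedence.

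**Step 3. Count the withhold cells in Appendix 13.4.** Pneumonitis 1, colitis/diarrhea 2, hepatitis 1, hypophysitis 1, nephritis 1, hypothyroidism 1, hyperthyroidism 1, dermatitis 1, neuromuscular 1, ocular 1, other 1.

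- Total: 1 + 2 + 1 + 1 + 1 + 1 + 1 + 1 + 1 + 1 + 1 = 12.
- Restart at Grade 1 or less: 10.
- Restart at Grade 1 or less, or baseline: 1 (hypothyroidism).
- Restart at Grade 2 or less: 1 (dermatitis).
- Cells that repeat the steroid taper: 0 of 12.

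The dermatitis restart grade stands alone. The missing taper does not: no cell has it.

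**Step 4. Ocular toxicity.** Both texts withhold at Grade 2, and both look for Grade 1 or less before restart. The only difference is the Appendix's 14-day stop. Illustration, with infusion on day 1: a Grade 2 event treated topically from day 2 reaches Grade 1 on day 18. That is 18 - 2 = 16 days, more than 14. The next infusion is due on day 1 + 21 = day 22. Read alone, 5.3.2 says the day 22 dose may be given; under the Appendix, treatment has already ended. A site that stops at 14 days breaks neither text.

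**The case against.** **Grade 2 may be deliberate.** The adjacent Appendix cell continues dosing for rash that never exceeds Grade 2, and 5.3.2 withholds for dermatitis only at Grade 3. Being 1 cell in 12 fits a skin-specific exception as well as it fits a slip. This stands, and it is why the fix offers two routes. It does not remove the conflict: if the exception is intended, 5.3.2 contradicts it.

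**The safety gap is narrow.** A reader might infer that the Appendix allows dosing while the subject is still on the 1-2 mg/kg/day steroid course given for Grade 3 dermatitis. The documents do not support that. The Appendix is silent on the taper in every cell, and silence does not cancel the 10 mg/day condition in 5.3.2. The gap is residual Grade 2 rash after taper, no wider.

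**The ocular difference looks like a second contradiction.** A reader might infer one, or might set 14 days against the nine-week delay limit in 5.3.2. Neither inference holds. Section 5.3.1 sends sites to the Appendix, 5.3.2 only permits restart, and both texts can be satisfied together. The two limits also run on different clocks: days on treatment for the event, and delay of the dose. What remains is a mandatory stop that the main lists do not repeat.

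**Discretion already allows caution.** Section 5.3.2, item 14, lets the investigator postpone treatment, and 4.3.1, item 8, allows a stop for "Other conditions that make study treatment continuation inappropriate judged by the investigator". True, but discretion lets a careful site hold; it does not give sites one rule.

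**Conclusion.** The dermatitis conflict is real and is in the current text. It affects one Appendix cell and one clinical situation: Grade 3 dermatitis that has improved to Grade 2, baseline Grade 0/1, steroid at 10 mg/day or less. In that situation one text holds the dose and the other permits it. The ocular point is secondary, an omission and not a contradiction. The documents give no event rates, so the number of subjects affected cannot be stated. There is no effect on ORR, and any effect on reporting is confined to descriptive safety tables. The conclusion assumes only that the taper condition in 5.3.2 continues to apply whichever restart grade is used.

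**What to change.** **Dermatitis.** Change the Grade 3 cell in Appendix 13.4 so that the hold lasts until the rash is at Grade 0/1 or baseline and systemic corticosteroid is at 10 mg/day prednisone equivalent or less. This matches 5.3.2 and brings the restart grade into line with the other 11 withhold cells. If the sponsor does intend Grade 2 for skin, leave the Appendix grade, state the exception in 5.3.2, and keep the taper condition.

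**Ocular toxicity.** In 5.3.2, item 10, add a cross-reference to the Appendix ocular row. Keep that row's full condition, including the reference to starting systemic treatment, because a shortened version would change the rule. State whether the 5.3.3 provision that lets the monitor and investigator decide for a subject who is benefiting applies to this 14-day stop.

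**Precedence.** Do not add a general clause that the stricter text wins. The Appendix's permanent-stop cells carry no benefit override, so such a clause could remove the one in 5.3.3 for every permanent-stop immune-related event. If a clause is wanted, limit it to restart conditions.

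**Cost.** Wording changes in a protocol amendment, with no new data. With the first dermatitis route, subjects with residual Grade 2 rash wait longer to restart, and a long wait counts toward the nine-week delay limit in 5.3.2, which can be waived after consultation with the medical monitor.

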2. OBJECTIVES AND ENDPOINTS			
8.3.2	Secondary Efficacy Endpoints	-	
8.7	EXPLORATORY ANALYSES		
SYNOPSIS	Inclusion Criteria / Exclusion Criteria	Inclusion Criteria:	
		"3. Subjects must have a histologically confirmed ENKTL at the study site。" is amended to	
		"Subjects must have a histologically confirmed	
4.1/4.2	Inclusion Criteria / Exclusion Criteria	ENKTL at the study site. Both nasal and non-nasal ENKTL are allowed."	
		Add " 6. Life expectancy ≥ 12 weeks."	
		"8. d) Serum creatinine $\leq 1.5 \times$ upper limit of normal	
		(ULN) or creatinine clearance ≥ 40 mL/min	
		(according to Cockcroft-Gault equation); e) Serum	
		total bilirubin $\leq 1.5 \times$ ULN;" is amended to "8. d)	
		Creatinine clearance \geq 40 mL/min (according to Cockcroft-Gault equation); e) Serum total bilirubin \leq	

$1.5 \times ULN$, unless considered to be due to Gilbert's
disease, where it must be $\leq 3 \times ULN$;"
Exclusion Criteria:
"1.Aggressive natural killer-cell leukemia." is
amended to "1. Aggressive natural killer-cell
leukemia or ENKTL patients who have any degree of
leukemic involvement will be excluded."
"3. Primary central nervous system lymphoma
(PCNSL) or secondary CNS involvement" is
amended to "3. Current or historical primary
central nervous system lymphoma (PCNSL) or
secondary CNS involvement."
"10. A known other malignancy within the past 5
years. Subjects with basal cell carcinoma of the skin,
squamous cell carcinoma of the skin, breast cancer
in situ, or cervical cancer in situ that have undergone
curative therapy are permitted to enroll" is amended to "10. A known additional malignancy within 5
years piror to the first dose of investigational
product. Subjects with locally curable malignancies
(including basal cell carcinoma of skin, squamous
cell carcinoma of skin, breast cancer in situ or
cervical cancer in situ, etc.) that have undergone
curative therapy are permitted to enroll"
"23. Subjects with a known history of alcoholism
or drug abuse." is amended to "23. Subjects with
active alcohol or drug dependence."
"25. Subjects with a history of psychiatric disease;
subjects with incapacity or limited capacity " is
amended to "25. Subjects with a history of

		psychiatric disease; or subjects with incapacity or limited capacity."	
SYNOPSIS	Primary efficacy analyses	"The statistical analysis will be performed by 24 weeks after the first dose of last subject. The median duration of follow-up of all responders since the time of first response is estimated to be around 23	Update statistical methods
8.3.1	Primary efficacy endpoints	months by that time, under an assumed enrollment rate of 1.5 subjects per month." is amended to "The statistical analysis will be performed by 24 weeks after the first dose of last subject."	
SYNOPSIS	Sample size	The primary efficacy endpoint is ORR assessed by IRRC according to Criteria for Response Assessment of Lymphoma: Lugano 2014 Classification.	
8.1	SAMPLE SIZE DETERMINATION		

SCHEDULE OF STUDY ACTIVITIES	Safety follow-up	"2. Safety follow-up: Adverse events (AEs) and concomitant medications can be collected by telephone follow-up at 60 days and 90 days after the last dose." is amended to"2. safety follow-up: It is	According to Protocol clarification letter dated 27 Jul 2020, clarify the safety follow-up
6.1.3.1	safety follow-up	recommended to 2. safety follow-up: It is recommended to complete all protocol required follow-up evaluations for the safety follow-up at 60 \pm 3days and 90 \pm 3 days after the last dose, or AEs and concomitant medications can be collected through phone call."	
SCHEDULE OF STUDY ACTIVITIES	Central pathology	Add: "Both fresh and archival biopsies are accepted and can be used by central pathology."	clarify the request of sample for central pathology
3.1.1	Screening		
6.1.1	Screening Central pathology		
6.3	PATHOLOGICAL ASSESSMENTS		
SCHEDULE OF STUDY ACTIVITIES	Bone marrow aspiration and biopsy	"21.Bone marrow aspiration and biopsy: Bone marrow aspiration and biopsy should be performed at screening for all subjects. Subjects with positive	Clarify that the bone marrow aspiration and biopsy should be performed when achieving CR/CMR, if the overall bone
6.1.2	Treatment Period, Bone marrow aspiration and biopsy		marrow assessment is indeterminate at screening
6.4	EFFICACY ASSESSMENTS	biopsy should be performed at screening for all subjects. Subjects with positive bone marrow aspiration/biopsy result or indeterminate overall bone marrow assessment at screening will undergo	

		bone marrow aspiration and biopsy when achieving CR/CMR based upon radiology for confirmation."	
SCHEDULE OF STUDY ACTIVITIES	Blood sample/ tumor tissue for biomarker testing	 "22.Blood sample for biomarker testing: A whole blood sample of 2 mL will be taken as genetic control in whole-exome sequencing for tumor tissue. View Central Laboratory Manual for details. Tumor tissue for biomarker testing: Seven (7) unstained tumor tissue sections are collected at screening for whole-exome sequencing of tumor tissue. View Central Laboratory Manual for details." is amended to 	To clarity that the samples for biomarker testing can be retrospective collected in study period.
		"22.Blood sample for biomarker testing: A total amount of 2 mL whole blood sample will be collected as germline control in whole-exome sequencing for tumor tissue. The whole blood can be collected at screening or retrospectively after study entry. View Central Laboratory Manual for details.	
		23.Tumor tissue for biomarker testing: Seven (7) unstained Formalin-Fixed, Paraffin-Embedded (FFPE) tumor tissue slides should be collected at screening for whole-exome sequencing of tumor tissue. If no samples were collected at screening, a retrospective collection of 7 archival FFPE tumor tissue slides is allowed. View Central Laboratory Manual for details."	
1.2.1.1	Pharmacodynamic Studies	Update the data of pharmacodynamic studies, details refer to Protocol Amendment 3.0	Data from pre-clinical pharmacodynamic studies were updated according to CS1001 IB v6.0.
1.2.2	Clinical Studies	Update the data of clinical studies, details refer to Protocol Amendment 3.0	Data from clinical studies were updated according to CS1001 IB v6.0.

3.1.1	Screening	 "At the screening phase, tumor tissue (7 evaluable unstained sections) and 2 mL of whole blood as genetic control in whole exome sequencing for tumor tissue" is amended to: "Seven (7) unstained FPPE tumor slides should be collected at screening for whole-exome sequencing of tumor tissue. A total amount of 2 mL whole blood should be collected at screening as germline control of whole-exome sequencing. If the tumor tissue and whole blood samples were not available at 	To clarity that the samples for biomarker testing can be retrospective collected in study period.
		screening, retrospective collections of 7 archival FFPE tumor tissue slides and collection of 2 mL whole blood are allowed for whole-exome sequencing"	
3.1.5	Treatment Beyond End of Study	Add "These subjects must provide written ICF and be willing and able to continue to follow all study procedures for continuing treatment."	According to Protocol clarification letter dated 27 Jul 2020, clarify the treatment beyond end of study

Confidential

		"	
5.3.2	Criteria for Dose Modification of Investigational Product	 Add"13.Any Grade 3 abnormal laboratory test result except for the following situations : Grade 3 hematologic toxicity. Study treatment will be delayed when Grade 2 hepatitis occurs. 14. Any AE, abnormal laboratory test result or intercurrent condition that in the investigator's opinion requires postponing study treatment." 	Clarity the laboratory and other criteria for dose modification of investigational product
5.3.3	Criteria for Permanent Discontinuation of Investigational Treatment	Add "Grade 4 abnormal laboratory test result except for the following situations: -Grade 4 neutropenia lasting for ≤ 5 days -Grade 4 lymphocytopenia or leukopenia -Solitary Grade 4 electrolyte disorder/imbalance that can be corrected by electrolyte supplementation/adequate treatment in 72 hours without any clinical consequence."	Clarity the laboratory and other criteria for permanent discontinuation of investigational product
6.6	Biomarkers	"Whole exome sequencing of tumor tissue: seven (7) unstained tumor tissue sections are collected at screening for whole-exome sequencing of tumor tissue; 2 mL of whole blood collected as genetic control." is amended to: "Whole exome sequencing of tumor tissue: seven (7) unstained FFPE tumor tissue slides should be collected at screening for whole-exome sequencing of tumor tissue; a total amount of 2 mL whole blood	To clarity that the samples for biomarker testing can be retrospective collected in study period.

	should be collected at screening as germline control of whole-exome sequencing.If the tumor tissue and whole blood samples were not available at screening, retrospective collections of 7 archival FFPE tumor tissue slides and collection of 2 mL whole blood are allowed for whole-exome sequencing."	
Throughout the document	 Administrative changes: Modifications to the heading and the texts Abbreviation list update Cross-reference update Typo and formatting update 	To increase protocol clarity, consistency and readability

Major amendments in protocol Version 2.0

Section(s)	Title of section(s)	Amendment details	Amendment rationale
SYNOPSIS	Study design and methods	The flow-chart: "safety follow-up: 30 days after the last dose of study treatment" is amended to "safety follow-up:30, 60, 90 days after the last dose of study treatment, Safety follow-up period refers to the 90 days after the last dose of the investigational treatment or the start of new anti-cancer treatment, whichever occurs earlier."	To clarify the safety follow-up timeframe.
SYNOPSIS	Exclusion Criteria (number 13)		To clarify the criteria of Chinese

4.2		"13. Any use of traditional Chinese medicines or herbal preparations within 7 days prior to the first dose of investigational product." is amended to "13. Any use of traditional Chinese medicines or herbal preparations with anti-tumor indications within 7 days before the first dose of investigational product"	medicines or herbal preparations in prior treatment in exclusion criteria.
SYNOPSIS			
SYNOPSIS	Statistical Methods	Update "Statistical Methods", detail refer to Protocol Amendment 2.0	Statistical methods were updated.
SCHEDULE OF STUDY ACTIVITIES	Safety follow-up (with footnote 2)	"safety follow-up: 30 days after the last dose of study treatment" is amended to "safety follow-up:30, 60 , 90 days after the last dose of study treatment, Safety follow-up period refers to the 90 days after the last dose of the investigational treatment or the start of new anti-cancer treatment, whichever occurs earlier."	To clarify the safety follow-up timeframe.
SCHEDULE OF STUDY ACTIVITIES	Concomitant medications (with footnote 5)	"All concomitant medications received from 30 days prior to the screening will be recorded until safety follow up is completed" is amended to "All concomitant medications received from 30 days prior to the screening will be recorded until 90 days after the last dose of study treatment or the start of new anti-cancer treatment, whichever occurs first"	According to Protocol clarification letter dated 17 Apr 2019, clarify the period for collection of concomitant medications.
SCHEDULE OF STUDY ACTIVITIES	PK (with footnote 18)	Add: "Blood samples for PK testing will be collected at the EOT visit, and safety follow-up visit at 30 days, and 90 days after the last dose of study	ADA sample should be always accompanying by PK sample
6.1.2.1	End-of-Treatment Visit	treatment."	simultaneously as reference of concentration data for justifying ADA
6.5	Pharmacokinetics and immunogenicity		result especially for negative result.

SCHEDULE OF STUDY ACTIVITIES 6.5	ADA (with footnote 19) Pharmacokinetics and immunogenicity	"Blood samples for ADA testing will be collected at EOT visit and safety follow-up visit" is amended to "Blood samples for ADA testing will be collected at the EOT visit and safety follow-up visit at 30 days, and 90 days after the last dose of study treatment"	Add ADA follow-up visit to follow ADA until the serum titers revert to baseline
SCHEDULE OF STUDY ACTIVITIES	Hematology, serum chemistry and urinalysis	Delete "bicarbonate"	According to Protocol clarification letter dated 07 Dec 2018, delete the collection of bicarbonate value
6.1.1			
6.2.4			
SCHEDULE OF STUDY ACTIVITIES 6.1.1	Bone marrow aspiration and biopsy	"Bone marrow aspiration/biopsy should be performed at screening. Subjects with positive bone marrow aspiration/biopsy result at screening will undergo bone marrow aspiration/biopsy when achieving CR based upon radiology for confirmation. Flow cytometry or immunohistochemistry (IHC) analyses can be used per investigator's judgment if bone marrow involvement cannot be determined under microscope." is amended to "Bone marrow aspiration and biopsy should be performed at screening for all subjects. Subjects with positive bone marrow aspiration/biopsy result at screening will undergo bone marrow aspiration and biopsy when achieving CR/CMR based upon radiology for confirmation. Immunohistochemistry (IHC) analyses should be performed under microscope no matter bone marrow involves or not (Suggest detecting CD56、TIA-1、CD3、GrB、perforin, and EBER hybridization in situ, etc.)."	According to Protocol clarification letter dated 08 May 2018, clarify the requirements for bone marrow aspiration and biopsy

1.1	DISEASE OVERVIEW	Update overview of indication, details refer to Protocol Amendment 2.0	Update the disease overview to provide more background information
1.2	MECHANISM OF ACTION	Update the information of approved anti-PD1/L1 antibody products, details refer to Protocol Amendment 2.0	Update the information about approved competitive products to provide more up-to-date information on the marketing status of these products
1.2.1.2	Pharmacokinetic Studies	Update the data of PK studies, details refer to Protocol Amendment 2.0 Data from pre-clinical Pl updated according to CS	
1.2.1.3	Safety Studies	Update the data of safety studies, details refer to Protocol Amendment 2.0	Data from pre-clinical safety studies were updated according to CS1001 IB v4.0.
1.2.2	Clinical Studies	Update the data of clinical studies, details refer to Protocol Amendment 2.0	Data from clinical studies were updated according to CS1001 IB v4.0.
3.1.3	Safety follow-up	"A safety follow-up visit should be conducted 30 days after the last dose of the investigational product." is amended to "A safety follow-up visit should be conducted 30, 60 , 90 days after the last dose of the investigational product. Safety follow-up period refers to the 90 days after the last dose of the investigational treatment or the start of new anti- cancer treatment, whichever occurs earlier."	To clarify the safety follow-up timeframe.
3.2.3	Rationale for Setting ORR as the Primary Endpoint	Update the rationale of ORR as primary endpoint selection of ORR as the primare endpoint	
4.5	Definition of Effective Contraception	Add "If total abstinence was used as highly effective method, other methods were no needed." According to Protocol clarification dated 17 Apr 2019, clarify the der of effective contraception	
5.4.2	Permitted Therapy	"Adrenal replacement with >10 mg corticosteroid per day or equivalent is permitted." is amended to	To correct a typo error.

		"Adrenal replacement with ≤ 10 mg corticosteroid per day or equivalent is permitted."	
6.1.2 6.4	Treatment Period EFFICACY ASSESSMENTS	"Bone marrow aspiration/biopsy should be performed at screening and when CR is achieved according to radiology. Flow cytometry or immunohistochemistry can be used per investigator's judgment if bone marrow involvement cannot be determined under microscope." is amended to "Bone marrow aspiration and biopsy should be performed. Immunohistochemistry (IHC) analyses should be performed under microscope no matter bone marrow involves or not (Suggest detecting CD56、TIA-1、CD3、GrB、perforin, and EBER hybridization in situ, etc.) "	According to Protocol clarification letter 08 May 2018, clarify the requirements for bone marrow aspiration and biopsy
6.1.3.1	Safety Follow-up	"Safety follow-up period refers to the 90 days after the last dose of the investigational treatment" is	According to Protocol clarification letter dated 17 Apr 2019, clarify the collection period of concomitant medications and clarify the safety follow up period.
7.1.3	Recording of Adverse Events	amended to "Safety follow-up period refers to the 90 days after the last dose of the investigational treatment or the start of new anti-cancer treatment, whichever occurs earlier."	
		Add "Concomitant medications are recorded until 90 days after the last dose or the start of new anti- cancer treatment, whichever occurs first."	
7.2.1	Definition of A Serious Adverse Event	"A SAE is defined as any adverse event that occurs from the time when subject signs the ICF to the time of end of post-treatment follow-up or PD (whichever occurs last), which meets any one of the following criteria:" is amended to "According to the definition from ICH (International Council for Harmonisation), SAE is any adverse medical event that meets any of the following criteria:"	According to the requirement of ICH guideline, update the definition of SAE
7.2.2	Serious Adverse Event Reporting	Update "Serious adverse event reporting"	According to Protocol clarification letter dated 17 Apr 2019, clarify the

7.5.2.1	Reporting of Pregnancy	Add "However, subjective induced abortion for pregnancy termination without medical reason does not need to be reported as a SAE of pregnancy termination."	requirement of SAE reporting and update the information of pharmacovigilance Clarify the criterion for reporting of pregnancy
8.1, 8.3 and 8.9	Sample Size Determination (8.1); Efficacy Analyses (8.3); and Interim Analysis (8.9)	Update statistical considerations and analysis plans, details refer to Protocol Amendment 2.0	Update sample size determination and efficacy analyses sections. Remove Section 8.9 as no interim analysis will be performed.
8.6	Immunogenicity Anslysis	Add "The treatment-induced ADA will also be analyzed by computing and reporting duration of an induced ADA response which will be classified as transient-positive ADA or persistent-positive ADA."	Clarify the analysis of transient-positive ADA or persistent-positive ADA
9.1	ETHICS COMMITTEE	"The EC is constituted in accordance with China Food and Drug Administration (CFDA) recommendations and" Is amended to "The Ethics Committee must be constituted in accordance with all applicable regulatory requirements and"	The constituent of EC need to meet the request of all applicable regulatory requirements
Throughout the document		 Administrative changes: Modifications to the heading and the texts Abbreviation list update Cross-reference update Typo and formatting update 	To increase protocol clarity, consistency and readability

Major amendments in protocol Version 1.1

Section	Title of section	Amendment details	Cause of amendment
1.2.2	Clinical Studies	"Up to now, no dose-limiting toxicity was observed in the dose- limiting toxicity study in a total of 6 subjects from 3 mg/kg and 10 mg/kg dose groups. The study showed overall good safety and tolerability" is amended to "To date (up to 13 February, 2018), no dose-limiting toxicity or treatment related serious adverse event was observed in the dose-limiting toxicity study in a total of 14 subjects from 4 groups including 3 mg/kg, 10 mg/kg, 20 mg/kg and 1200 mg fixed dose group. The study showed good overall safety and tolerability."	Data from phase I trial was updated.
3.1	Overall Design	"At the screening phase, tumor tissue (7 evaluable unstained sections) and 9 mL of peripheral blood will be collected for biomarker investigation." is amended to "At the screening phase, tumor tissue (7 evaluable unstained sections) and 2 mL of whole blood as genetic control in whole exome sequencing for tumor tissue."	The immune repertoire assay of peripheral monocytes is not required, and therefore there's no need for taking peripheral blood sample of 7 mL.
3.1.2.1	Treatment Beyond Disease Progression	The following paragraphs are added: "In special situations, a subject with disease progression confirmed by radiology or other clinical examinations who will possibly benefit from further investigational treatment may continue the treatment at the judge of investigator in consultation with the sponsor. A written consent from the subject must be obtained before any treatment beyond progression (including suspected pseudoprogression and confirmed disease progression)."	According to feedback from investigators and clinical study results of drugs of a similar target, in special cases, a patient may continue to benefit from the investigational treatment despite disease progression confirmed by radiology or other clinical examinations. In the protocol, a written consent is required for a subject to receive treatment beyond definite disease progression.
4.1.1	Inclusion Criteria	"With disease progression as the best response to the last line of therapy, or progression following response or stable disease achieved after the last line of therapy" is amended to "relapse: disease progression after response to the last treatment; refractory: no response to the last treatment".	According to input from clinicians and designs of similar studies, patients who are non-responders to the last treatment may be enrolled in the clinical trial.

